3.0 Objectives

SPECIFIC AIMS

Degenerative disease of the lumbar spine (e.g., degenerative discs and facets, bulging discs) is ubiquitous in older adults, but low back pain is not.^{1,2} Treatment that focuses exclusively on degenerative spine disease such as spinal injection and surgery, therefore, has resulted in rising costs and exposure to potentially life-threatening morbidity but not improved outcomes.³ We posit that to improve treatment outcomes for older adults with chronic low back pain (CLBP – back pain that has been present on at least half the days for at least 6 months⁴), the condition should be approached as a syndrome, that is, a final common pathway for the expression of many contributors. Geriatricians evaluate and treat other syndromes, such as delirium and falls similarly, with good outcomes.⁵ When an older patient experiences delirium, a geriatrician doesn't recommend brain surgery. Using this model, the lumbar spine is considered a weak link, but is rarely the sole treatment target. Conditions that commonly contribute to pain and disability in older adults with CLBP such as hip osteoarthritis (OA), fibromyalgia, and depression, are associated with specific evidence-based treatments.

PURPOSE AND HYPOTHESES

The central question that the proposed randomized trial is designed to answer is: **What is the efficacy of comprehensive patient-centered care of CLBP as a syndrome that is delivered in Aging Back Clinics (ABC), compared with usual care (UC)?** Through prior VA Rehabilitation Research & Development support, we have developed and published evidence and expert-opinion based guidelines for the evaluation and treatment of 12 key contributors to pain and disability in older adults with CLBP – hip OA, fibromyalgia, myofascial pain, lumbar spinal stenosis, sacroiliac joint syndrome (SIJS), leg length discrepancy, lateral hip/thigh pain, insomnia, depression, anxiety, maladaptive coping, and dementia.⁶⁻¹¹ Our prior work also supports the commonplace nature of multiple contributors to CLBP in older Veterans and the feasibility of delivering ABC care that follows our published guidelines. We now wish to compare this approach to that of UC in older Veterans. Proof of the hypotheses that we will test could significantly

impact patient care by reducing pain and disability and avoiding costly and potentially morbid treatments. The proposed trial is designed to address the following aims:

Aim 1: Establish the efficacy of ABC care compared to usual care.

We hypothesize that those randomized to ABC care will have:

H1.1: Greater 6-month reductions in pain-related disability as measured by Oswestry Disability Index (ODI; primary outcome and endpoint);

H1.2: Greater 12-month reductions in ODI; and greater 6- and 12-month reductions in pain severity (by PROMIS 29), quality of life (by PROMIS Global Health [GH]); depressive and anxiety symptoms (by PROMIS 29); and greater improvement in falls efficacy (by Falls Efficacy Scale-International short form);

H1.3: Less healthcare utilization between 6 and 12 months with respect to emergency room visits, hospitalizations, opioids prescribed, and invasive procedures performed (secondary outcomes and endpoints).

Aim 2: Explore the heterogeneity of treatment efficacy of ABC care.

H2.1: Those with greater baseline CLBP-associated disability, anxiety/depression, mild cognitive impairment, and/or obesity will reap greater benefits from ABC compared to UC (exploratory subgroup discovery).

Four hundred fifty Veterans age 65-89 with CLBP, (for a targeted enrollment of 310), will be recruited from primary care provider (PCP) practices at 3 VAs – VA Pittsburgh Healthcare System, VA Greater Los Angeles, and Hunter Holmes McGuire (Richmond) VA. Individuals will be randomized to receive either ABC care or UC, and they will be followed for one year. Aging Back Clinics will be staffed by consultants (e.g., geriatrics, pain medicine, rheumatology) that have been trained in evaluating and treating key CLBP conditions associated with our published evidence-based algorithms. Usual care will not be constrained. Baseline measures will be assessed on site or on the telephone and include: Minimal Data Set recommended by the NIH Task Force on research standards for CLBP⁴; Oswestry Disability Index (ODI; main outcome)¹²; cognitive function (QMCI)¹³; PROMIS-29 that includes pain severity, pain-related activity interference, physical function, sleep disturbance, depressive symptoms, leg symptoms¹⁴; quality of life with the PROMIS-GH scale¹⁵, participant opioids-related concerns with the Prescribed Opioids Difficulties Scale¹⁶, gait speed, balance confidence with the Falls Efficacy Scale-International short form¹⁷; healthcare utilization over the prior month (e.g., pain medications, emergency room visits, hospitalizations) will be assessed on site. We will also be utilizing the Life Space Assessment¹⁰⁶ to measure the spatial extent of a participant's mobility. Three, 6-, up to 9-, and 12-months outcomes (ODI, PROMIS 29 and GH, balance confidence, healthcare utilization, life space assessment and VR-12) will be assessed over the telephone by individuals masked to group assignment. While monthly, the 0-10 Numerical Pain Rating Scale, Medications (pain medications monthly and all medications at baseline and final follow-up), and Health Care Utilization will be measured. The Global Impression of Change data measure will be administered only at the final phone follow up. The proposed clinical trial has the potential not only to improve pain-related disability, but also to reduce morbidity, increase quality of life, and limit healthcare utilization.

5.0 Study Procedures

5.1 Study Design

RESEARCH DESIGN AND METHODS

The proposed clinical trial is designed to evaluate the efficacy of Aging Back Clinics (ABCs) that approach CLBP in older Veterans as a geriatric syndrome, that is, a final common pathway for the expression of multiple contributors, as compared with Usual Care (UC). In the context of the research proposed, **ABCs are virtual interdisciplinary clinics** that are inserted within the stepped care model shown in Figure 4. Veterans without red flags requiring urgent attention are referred for ABC care that will be **delivered by a specialist provider** that has been trained in use of the algorithms. Both ABC care and UC will be provided for up to 12 months. Those with refractory symptoms may be referred for intensive interdisciplinary pain rehabilitation,

depending on their availability and the Veteran's capacity to participate.

Interventions for ABC care participants are numerous and vary depending on participants' needs. These interventions include but are not limited to CBT, pharmacotherapy, physical therapy (PT), exercise therapy, analgesia, orthotics, injections, and acupuncture. One of the primary goals of ABC care is to avoid unnecessary and costly imaging and the risks associate with it, including unnecessary, ineffective, and potentially morbid surgeries.

[figure not shown]

Figure 4. The ABC Stepped Care Approach

The conditions targeted by ABCs include those that cause CLBP directly (hip OA⁶⁶, SIJS⁶⁸, myofascial pain⁶⁷, lumbar spinal stenosis⁶⁹, leg length discrepancy⁵⁴); those that impair pain modulation, compound CLBP-associated disability and that themselves can cause disability (fibromyalgia³⁰, depression²¹, anxiety²¹, maladaptive coping [i.e., pain catastrophizing⁷¹ and/or fear avoidance beliefs⁷⁰], insomnia²³, dementia⁷²); and those that can mimic radiculopathy (greater trochanteric pain syndrome⁷³, myofascial pain⁷⁴). While our screening procedures exclude Veterans with possible dementia (based on the Mini Mental State Examination), those with possible mild cognitive impairment (MCI) will be included. As MCI and dementia are on a continuum, providers may wish to apply elements of the published Dementia protocol to those that screened positive for MCI.

Participants:

About 450 Veterans (150 from each site), age 65-89 with chronic low back pain (CLBP) will be recruited, (to target randomizing 310 participants), from the VA Pittsburgh Healthcare System (VAPHS), the VA Greater Los Angeles Healthcare System (Los Angeles, CA), and the Hunter Holmes McGuire VA Medical Center (Richmond VA). We anticipate the need to telephone screen ~1050 (i.e., ~175 per site per year) to obtain 450 participants who meet all inclusion and exclusion criteria. No one will be excluded on the basis of race, gender or ethnicity. Based upon the data from each of the three sites, we anticipate that our overall participant sample will be 97% male, 3% female, 2% Hispanic or Latino, 98% Not Hispanic or Latino, 1% American Indian/Alaskan Native, 0% Asian, 2% Native Hawaiian or Pacific Islander, 18% Black or African American, and 79% White or Caucasian. Non-Veterans will not be recruited to participate. Vulnerable subjects will not be enrolled, including children and prisoners. Neither pregnant subjects nor women of childbearing potential will be included because we are targeting older adults with chronic LBP.

Costs and Payment:

In order to compensate participants for their time, they will be paid \$100 in total, with payments spaced out over 12 months. They will be paid \$40 for their baseline visit and \$30 for their final follow-up visit. An additional \$30 will be paid after their 6-month follow-up call.

Participants will be paid by check or electronic bank deposit, \$100 in total, with payments spaced out over up to 12 months. They will be paid \$40 for their baseline visit and \$30 for their final follow-up visit. An additional \$30 will be paid after their 6-month follow-up call. Participants may drop out of the study at any time without forfeiting the payments they have already received. Payments typically take between 10 days and two weeks to reach Veterans.

5.2 Recruitment Methods

Recruitment Procedures: We will recruit 450 participants with methods that we have used successfully for other VA clinical trials:

1. We will request a waiver of informed consent to review the CPRS records of Veterans age 65-89 with a documented diagnosis of low back pain. The research coordinator (RC) at each site will review records of potentially eligible Veterans to ensure the veteran has a primary care provider within the VA system and that they have seen their PCP within the past 6 months for low back pain. This pull of potential eligible participants will initially be extracted from the Corporate Data Warehouse by a study staff member. Potentially eligible Veterans will be mailed a letter signed by the site PI and a flyer or brochure describing the study (both of which will be IRB-approved). If (s)he is interested in participating, (s)he will call the study research coordinator (RC), whose name and contact information will be provided in the brochure. In addition, 14 days after we have mailed letters, if we have not been contacted, we will call potential participants to ascertain their interest in participation. We have successfully adopted this strategy in the context of our ongoing pilot study.
2. We will recruit directly from clinics, at each local VA site, using the following approaches: a) Site PIs will send email to the Providers in clinics at their site to introduce the study. b) Brochures will be delivered to clinic waiting rooms and to the Providers themselves including those associated with Women's Health Clinics. We will suggest that Providers keep brochures in their exam rooms for distribution to potentially eligible Veterans. c) IRB-approved posters will be placed in exam rooms. d) Site PIs will deliver an educational presentation on CLBP for PCPs and/or Providers in the context of an existing conference, and study information will be provided at that time.
3. The IRB-approved brochures will also be placed in waiting rooms of specialty clinics that commonly care for Veterans with CLBP (e.g., orthopedics, neurosurgery, neurology, pain medicine). Interested Veterans will call the RC to complete screening procedures.

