The 2017 Clinical Practice Guideline on Acute, Subacute and Chronic Low Back Pain from the American College of Physicians (ACP) approach CLBP as a non-specific condition and recommend “treatment with nonsteroidal anti-inflammatory drugs (NSAIDs) as first-line therapy” for patients “who have had an inadequate response to nonpharmacologic therapy.”²⁸ Even these recent guidelines fail to acknowledge that NSAIDs are very cautiously recommended for chronic use in older adults because these drugs risk causing renal insufficiency, gastrointestinal bleeding, and other adverse events.²⁴ The guidelines also recommend initial treatment of CLBP with multidisciplinary rehabilitation (MR) as one non-pharmacological option based on moderate quality evidence²⁸, even though these programs are characterized by high participant burden, making them inaccessible to many older Veterans, especially those who are physically and/or cognitively frail. Evidence indicates that **while MR improves function, it is only modestly effective in reducing pain intensity**³², **one of the key outcomes that our patients value**. As noted above, older adults with CLBP can have many physical contributors to their pain³³ that have specific evidence-based pain treatments and may not be included in MR programs, as these programs tend to be group based, not individualized. Thus, approaching CLBP as a non-specific condition is fraught with limitations that result in suboptimal outcomes for many older adults.

How can we redirect the evaluation and treatment of older adults with CLBP to result in better outcomes? To answer this question, we started by convening an expert panel of three physical therapists (PTs) and a geriatrician/ rheumatologist whose practices focused on chronic pain management. The panel’s task was to **identify common categories of physical pathology in older adults with CLBP that were not being treated because they were overlooked or misdiagnosed** by referring providers. Four categories were identified: myofascial pain (MP), fibromyalgia, sacroiliac joint syndrome (SIJS), and hip disease.³³ We developed protocols to identify these conditions and established the feasibility of training providers in their recognition.³³ We found that MP exists in 96% of older adults with CLBP, SIJS in 84%, hip disease in 24%, and fibromyalgia in 19%. Eighty-two percent had multiple conditions³³, none diagnosed with spinal imaging, but all detectable during a thorough history and physical exam.

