Randomization and Blinding: Following baseline testing, we will use the high quality pseudo-random deviate generator in SAS® (SAS Institute, Inc., Cary, North Carolina) to randomize participants to ABC care or UC in a 1:1 ratio, stratified by recruitment site. Within each site, we plan a blocked randomization scheme to force continued approximate balance between the numbers of subjects in each arm during recruitment. The block size will be randomly chosen to be one of two small even numbers to prevent personnel from predicting treatment arm, and exact block sizes will be revealed at the study conclusion. The study statistician will create separate randomization schedules for the 3 strata that contains a randomization sequence number (different from a participant's study identification number) and assigned arm. Then he will create a series of sealed envelopes for each of the sites containing the treatment assignment but conspicuously labeled on the outside with only the randomization sequence number. At the time of randomization, the overall RC based at the coordinating site will open the next available envelope specific for the participant's site, and record the randomization sequence number, subject identification number and group assignment in a dedicated database, different from the main study database. She will then inform the RC at the participant's site of their randomization group and the local RC will inform the participant of next steps. Personnel assessing follow-up outcomes will be masked to intervention assignment (see Follow-Up below). The study statistician has successfully employed the same process in other clinical trials.

Intervention

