UC will not be constrained. As a courtesy, participants who are randomized to UC will be offered the ability to see an ABC provider at their site (in person or virtually) after their completion of all study related procedures and the end of their up to 12 month participation. The RCs will track the components and location of care with monthly telephone calls using methods that we and others have used successfully in older adults (see below). We considered other control group designs, but chose not to for the following reasons: 1) Our clinical experience in delivering care to older Veterans with CLBP in our pain clinics highlights that most patients with CLBP already have had and failed a trial of physical therapy; thus, while we considered a control condition of physical therapy and analgesics, patients' prior participation in physical therapy would threaten recruitment feasibility. 2) We considered physical therapy and analgesics for the control group, and altering our inclusion criteria; specifically, we considered including only Veterans with "new onset" CLBP, e.g., back pain on most days for no more than the prior 12 months to reduce the likelihood of prior physical therapy; had we used these criteria in our previously described pilot work, however, only 4 of 50 participants would have qualified. 3) We considered recruiting patients from pain clinics, i.e., randomizing participants to either ABC care or Pain Clinic care, but the numbers of Veterans referred to Pain Clinics is considerably smaller than those available with our strategy. Comparing ABC care to standard Pain Clinic care could be the focus of a much larger, future trial.

ABCs will be staffed by a minimum of 3 non-surgical consultants at each site who have been trained in the published evaluation and treatment protocols. The PI will train providers at VAPHS and the Greater Los Angeles VA on site. Those at the Richmond VA site will be trained by co-I [name] (Richmond site PI) who has been trained in the context of the VA Rehab R&D-funded pilot studies that form the foundation of the proposed clinical trial. Training at all sites will occur over one day and will use effective adult learning principles that we have successfully employed in our pilot studies (see Preliminary Studies). Learning will be interactive and characterized by goal-directed practice coupled with targeted feedback^{93,94} as follows:

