The ABC Clinic operations will be overseen by the Local Site PI and the Local Site RC. The RC will be responsible for maintaining the clinic schedule (i.e., scheduling all appointments and any changes to the schedule). The Local Site PI will be the ABC Clinic Director. The RC will schedule appointments with the ABC clinic providers and ensure that those assigned to UC do not have appointments with the ABC providers for the duration of the study. Day to day procedures for operationalizing this process will be finalized during the study start-up period at each site.

Communication also will occur between ABC Clinic Providers and other relevant clinic providers that are consulted in the context of the algorithms. This will occur in the same manner as per standard VA care. That is, consultations will be ordered through CPRS and all patient-related communications will occur securely through CPRS.

Recurring Meetings

The Overall PI and the Overall RC will meet weekly to discuss overall and site-specific activities, including recruitment, enrollment, retention, and any additional study activities or concerns. Additional meetings will be conducted as the need arises. The RC will take notes and keep those records for the duration of the study.

The Overall PI, Overall RC, Local Site PIs and RCs will meet weekly via teleconference during project start-up and the first six weeks of recruitment. Then, meeting frequency will be monthly or as needed for the duration of the project. During the first three months of recruitment, they will discuss recruitment strategies, progress, and ensure adherence to the protocol. For the duration of the study, the calls will focus on responding to local site PI/RC questions, discussing recruitment goals and actual recruitment, as well as retention, enrollment, and follow-up progress. Notes will be taken by the Overall RC and kept for the duration of the study.

The Overall PI, the Local Site PIs, and all ABC clinic providers will communicate during regularly scheduled meetings. During project start-up, the Overall PI will meet with the Local Site PIs and ABC clinical providers to review 2-3 algorithms per week. During the first 6 weeks of participant enrollment, weekly meetings will continue, and specific participant cases will be discussed. Providers will present cases which allow for discussion on adherence to and reinforcement of the published algorithms. Subsequently these meetings will occur monthly or on an ad hoc basis.

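### The site PI, who directs the ABC clinic, is to give PCPs a CLBP talk with no limit on its content: an avoidable risk, of unknown size, of contaminating usual care

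*Combined protocol and SAP*

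**What the plan says.** Section 5.2 (Recruitment Methods) lists, under direct recruitment from clinics, item 2(d): "Site PIs will deliver an educational presentation on CLBP for PCPs and/or Providers in the context of an existing conference". Study information is to be given on the same occasion, so the talk is clinical education with study information added. The section does not give its content, its timing, how often it is held or who attends.

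Section 8 (Communication Plan) states: "The Local Site PI will be the ABC Clinic Director". The speaker therefore runs the intervention at that site.

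Section 3.0 says that participants "will be recruited from primary care provider (PCP) practices at 3 VAs". In the record review of section 5.2, coordinators check records "to ensure the veteran has a primary care provider within the VA system" and that this provider was seen for low back pain within the past 6 months.

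Section 5.5 says that the statistician will "randomize participants to ABC care or UC in a 1:1 ratio, stratified by recruitment site". Allocation is by individual, not by PCP or practice. On the comparator, the same section says: "UC will not be constrained".

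The one stated safeguard is in section 8, where the coordinator is to "ensure that those assigned to UC do not have appointments with the ABC providers for the duration of the study". Section 5.5 also has the components of care tracked monthly in both arms.

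**The concern.** Part of what ABC adds is knowledge held by the treating clinician. Section 2.0 describes the founding task of the programme, with referring providers in mind: "identify common categories of physical pathology in older adults with CLBP that were not being treated because they were overlooked or misdiagnosed". A talk on CLBP by the ABC director to the PCPs who look after UC participants could pass on some of that knowledge.

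Because randomization is within site and by individual, a PCP who hears the talk may treat participants in either arm. UC participants have more to gain from a better-informed PCP, since ABC participants already receive that content from a trained specialist. Any effect would therefore probably shrink the ABC minus UC difference. This applies to the 6-month ODI and to the utilization outcomes in H1.3, such as opioid prescriptions and invasive procedures, which depend partly on PCP prescribing and referral.

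The trial itself would create this exposure. That sets it apart from the background exposure that comes from the algorithms having been published.

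**Working it through.** **Is the route open?**

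1. Speaker: the site PI, who is the ABC Clinic Director (sections 5.2 and 8).
2. Audience: PCPs and/or other clinic providers at the site (section 5.2), where participants' PCPs practise (sections 3.0 and 5.2).
3. Allocation: by individual within site (section 5.5), so one PCP can have patients in both arms.
4. Safeguard: it covers UC appointments with ABC providers (section 8). It does not cover what PCPs are taught.
5. Analysis: care is tracked monthly (section 5.5), but section 5.6 plans no analysis of drift in UC.

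The route is open. How much would pass along it is not stated anywhere.

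**How much reserve does the plan have?**

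Inputs from the sample size paragraph of section 5.6: difference 7 ODI points, SD of change 18, two-sided alpha 0.05, 310 randomized, 280 completers (140 per arm), power 90%.

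Standard error of the difference = 18 × √(2/140) = 2.151.

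Power ≈ Φ(difference / 2.151 − 1.960).

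*Plan's own figure:* 7 / 2.151 = 3.254, less 1.960 = 1.294, and Φ(1.294) = 0.902. The noncentral t calculation gives 0.900. The stated 90% is reproduced.

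*Smallest difference detectable with 90% power:* (1.960 + 1.282) × 2.151 = 6.97 points, against the 7 planned.

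*Attenuation.* The documents give no uptake figure, so the first column is an assumption.

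| Assumed attenuation | Difference left | Power, normal | Power, t | Completers for 90% (normal) |
|---|---|---|---|---|
| 0% | 7.00 | 0.902 | 0.900 | 278 |
| 5% | 6.65 | 0.871 | 0.869 | 308 |
| 10% | 6.30 | 0.834 | 0.831 | 344 |
| 15% | 5.95 | 0.790 | 0.787 | 386 |

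*What the attenuation column means.* It is an average over the whole UC arm: attenuation = (share of UC participants whose PCP attended) × (share of the full ABC effect passed to those participants). If half of the PCPs attended, 15% average attenuation requires 0.15 / 0.5 = 30% of the ABC effect to pass through the talk, and 5% requires 0.05 / 0.5 = 10%.

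*Side note.* The stated 15% dropout leaves 310 × 0.85 = 263.5 completers, not 280. At 264 completers the normal-approximation power for 0%, 5%, 10% and 15% attenuation is 0.885, 0.851, 0.812 and 0.766. That mismatch is a separate matter, and the point here does not depend on it.

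**The case against.** The strongest reply is that a conference talk is not ABC care. Section 5.5 describes ABC as care by trained specialists. They have a day of hands-on training with patients, followed by 4 to 5 weeks of algorithm teleconferences. They use a structured examination, the Take Back Your Back tool, a booklet, a workbook and templated follow-up. The only evidence of changed practice (section 2.0, Pilot Study #1) came from four providers after two training sessions. Section 5.5 also says that PCPs have short appointments and often cannot address chronic pain adequately. All of this stands, and it argues for a small effect. It protects prescribing and referral less well, because those choices do not need a long visit.

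A second reply is that UC is deliberately unconstrained, the algorithms are already published, and the same PCPs may also treat ABC participants. The first two points show that some exposure belongs to usual care anyway, but the talk is exposure added by the trial. The third means that the talk is not confined to the control arm, which is why the direction of bias is probable and not certain.

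A third reply is that direct crossover is barred and care is tracked monthly. Both are useful. Neither limits what PCPs are taught, although the tracking would allow drift to be described.

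A reader might infer that the talk does deliver part of ABC to UC, that it reaches every UC patient of an attending PCP, or that the comparator is no longer usual care. The documents support none of these: the content, timing and attendance of the talk are not given.

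**Conclusion.** The concern holds as a risk. The plan schedules CLBP education, by the head of the intervention clinic, for clinicians who may deliver the comparator. It sets no limit on content and has no safeguard for this route. Any bias is probably toward no difference, and its size is unknown.

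The risk deserves attention because the plan's own calculation leaves about 0.03 of an ODI point in hand (7 − 6.97). An assumed attenuation of 5% to 15% takes power from 90% to about 87% to 79%. At the low end the loss is modest, and at the high end the talk would have to be quite influential. These figures rest on the plan's SD of 18, its 280 completers, and a two-group comparison of change scores. The planned model also adjusts for baseline ODI; any gain from that is not quantified in the plan and is not counted here.

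This is worth changing because it is cheap and avoidable. It is not evidence that the comparison is already compromised.

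**What to change.** Reword section 5.2, item 2(d), along these lines: until the last participant's final follow-up, presentations to PCPs and clinic providers cover study information (purpose, eligibility, how to refer) and do not teach the ABC structured examination, contributor screening or treatment algorithms. That material is offered to the sites after follow-up closes.

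If talks have already been given, record their content, dates and attendance. State in section 5.6 that ABC-type care in the UC arm will be described from the monthly utilization data. This needs no new data collection from participants.

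The cost is one clause, a somewhat less attractive talk and possibly slightly fewer PCP referrals. Mailed letters with follow-up calls, and clinic brochures and posters, remain as recruitment routes. Table 3 projects 1,194 + 1,828 + 1,035 = 4,057 eligible Veterans per year. These are potential enrollees, not consenting ones, so the table does not prove that recruitment could do without the talk. The change keeps the talk and narrows only its content.
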